### 8.13 IV infusion-related reaction and other hypersensitivity events

If a subject experiences CTCAE Grade  $\geq 2$  anetumab ravtansine infusion reaction or other CTCAE Grade  $\geq 2$  hypersensitivity event deemed at least possibly related to anetumab ravtansine, the infusion of anetumab ravtansine will be held. In case of a CTCAE Grade 2 or 3 event, anetumab ravtansine treatment may be restarted at the time determined at the investigator's discretion. In case of a CTCAE Grade 4 event, anetumab ravtansine treatment should be permanently discontinued

### 8.14 Miscellaneous

Any drug-related CTCAE Grade  $\leq 2$  TEAE thought to be at least possibly related to anetumab ravtansine that, in the investigator's opinion, is thought to require treatment modification. Such TEAEs might be CTCAE Grade  $\leq 2$  toxicities, which interfere with daily life activities, such as long lasting fatigue, anorexia, or corneal toxicity.

### 8.15 Anetumab ravtansine treatment modification due to corneal epitheliopathy

The Bayer Severity Grading system will be used to assess the severity of TEAEs of corneal epitheliopathy and BCVA changes (attached table). The worst Bayer severity grade in the worst eye will be considered as the overall grade of corneal epitheliopathy for the purpose of treatment modification decisions.

TEAEs of corneal epitheliopathy (confirmed by slit lamp biomicroscopy examination that are deemed to be at least possibly related to anetumab ravtansine should be managed according to the principles for the modification of anetumab ravtansine treatment due to this type of TEAE (i.e., no change, temporary treatment interruption, dose reduction, or permanent discontinuation of treatment) outlined in the attached table below. Treatment modification decisions should be based only on the severity of corneal epitheliopathy and not the severity of BCVA changes (attached table).

#### **Bayer classification and management of corneal epitheliopathy**

| Toxicity (worst grade, worst eye) | Corneal morphology changes   | Anetumab ravtansine interruption and dose reduction   | Remedial eye treatment a  |
|--|---|--|---|
| Grade 0                                  | No pathologic changes   | No change/continue treatment   | Treatment with ophthalmic lubricants b   |
| Grade 1                                  | Treatment-emergent superficial punctate keratitis (SPK) (new or worsening by $\geq 2$ grades) | no change/continue treatment   | Treatment with ophthalmic lubricants should be used. Topical steroids may be added. b                          |
| Grade 2                                  | Epithelial opacities
Corneal microcysts or microdeposits                                   | Treat on time at the same dose if ophthalmological exam can be performed as frequently as prescribed | Intensive treatment with ophthalmic lubricants (may be enhanced with ointments b ). Topical steroids should be |

|  |   |   |  |
|--|---|---|--|
|  | Corneal erosion
Stromal opacity
(non-central)                         | by the investigator.
If ophthalmological exam cannot be performed as frequently as prescribed by the investigator, treatment may be held until the event has resolved to the acceptable severity level. b
The event must resolve to acceptable level within 6 weeks after the last dose. c, d
Treatment may be restarted at the same dose or at the dose reduced by 1 level. b, c                             | added.
Therapeutic contact lenses may be used. b   |
| Grade 3  | Corneal ulcer without risk of acute rupture
Stromal opacity
(central) | Treatment should be held until the event has resolved to the acceptable severity level. b
The event must resolve to acceptable level within 6 weeks after the last dose. c, d
Treatment should be restarted at the dose reduced by 1 level. e
If Grade 3 corneal morphology change occurs again after dose reduction, the current dose should be reduced by 1 level or permanently discontinued. b | Intensive treatment with ophthalmic lubricants, enhanced with ointments. Topical steroids should be added.
Therapeutic contact lenses or eye occlusion are recommended. b  |
| Grade 4  | Corneal ulcer more severe than Grade 3                                      | Permanently discontinue treatment.  | Intensive treatment with ophthalmic lubricants, enhanced with ointments, should be used.
Topical steroids should be added.
Topical antibiotics may be added. b
Therapeutic contact lenses or eye occlusion are recommended. b
Amniotic membrane transplant and other locally approved treatments may be used. b |
| 
a Other remedial therapies for corneal epitheliopathy may be added or substituted at investigator's discretion or according to the institutional guidelines.
 
b At the investigator's (and / or the ophthalmologist's) discretion.
 
c Worsening or resolution of corneal epitheliopathy must be confirmed by slit lamp biomicroscopy.
 
d Treatment may be restarted at the investigator's discretion even if the epitheliopathy change has resolved
 
to the acceptable severity level >6 weeks after the last dose, if the investigator in consultation with the
 |   |   |  |

sponsor deems that continued treatment is appropriate based on the investigator's assessment of the benefit-risk ratio.

e Anetumab ravtansine dose reduction by 1 dose level translates to a change from 6.5 mg/kg Q21D to 5.5 mg/kg Q21D or from 5.5 mg/kg Q21D to 4.5 mg/kg Q21D. Dose reductions of anetumab ravtansine are permitted for as long as the continuation of treatment is appropriate based on the investigator's assessment of the benefit-risk ratio.

### **Recommendations for changes in tear production and intraocular pressure (IOP)**

Reduced tear production is a risk factor for developing ocular surface disease, including corneal epitheliopathy. Therefore, tear production will be evaluated by Schirmer's test in this study to determine if changes in this parameter may be helpful to identify subjects at higher risk of developing corneal epitheliopathy.

Treatment-emergent abnormal values in the Schirmer test (dry eye) should be evaluated and managed by an ophthalmologist to provide adequate protection to the corneal epithelium.

Remedial therapy for treatment-emergent changes in Schirmer test (dry eye) should be chosen at the investigator's discretion or according to institutional standards. These measures may include topical lubricants such as eye drops and ointments, punctal occlusion, use of therapeutic contact lenses, and / or any other locally approved treatment chosen at the discretion of the investigator and the ophthalmologist. Ophthalmological monitoring should be maintained until changes in the Schirmer test (dry eye) have resolved.

Increases in the intraocular pressure (IOP) may occur in some subjects with corneal epitheliopathy as a consequence of remedial therapy with topical steroid eye drops. Because this treatment may be required for adequate remedial treatment of corneal epitheliopathy, IOP will be monitored during this study.

Treatment-emergent changes in IOP should be evaluated and managed by an ophthalmologist.

Remedial therapy for IOP changes should be chosen at the investigator's discretion or according to institutional standards. These measures can include modification of the type or posology of topical steroid eye drop, initiation of topical IOP lowering drugs, or any other locally approved treatment chosen at the discretion of the investigator and the ophthalmologist. Ophthalmological monitoring should be maintained until IOP changes have resolved.

#### **8.16 Continuation of anetumab ravtansine after treatment modification**

Anetumab ravtansine treatment may be restarted at the appropriate dose if the TEAE requiring treatment modification has resolved to CTCAE Grade 1. Treatment modification (epitheliopathy) within 42 days after the last dose of anetumab ravtansine (i.e., the next scheduled dose would be delayed by  $\leq 21$  days).

If treatment modification of anetumab ravtansine is caused by a hematological TEAE, and the continuation of treatment is appropriate at investigator's discretion, the anetumab ravtansine dose will be adjusted as described in table below.

#### **8.17 Anetumab ravtansine dose adjustments in response to neutrophil and platelet nadir counts of the previous cycle:**

| CTCAE System/Organ/Class (SOC)       | GRADE   | ADVERSE EVENT   | AGENT               | ACTION**              |
|--------------------------------------|---------|---|---------------------|-----------------------|
| INVESTIGATIONS                       | Grade 2 | Neutrophil count decrease >500 or <500 for <7 days AND Platelet count decreased $\geq$ 25,000   | Anetumab ravtansine | No change             |
| INVESTIGATIONS                       | Grade   | Neutrophil count decrease <500 for $\geq$ 7 days AND Platelet count decreased <25,000 for $\geq$ 7 days with or without active bleeding, OR <50,000 for $\geq$ 7 days with clinically significant bleeding b | Anetumab ravtansine | Decrease 1 dose level |
| BLOOD AND LYMPHATIC SYSTEM DISORDERS | Grade 3 | Febrile neutropenia AND Platelet count <25,000 for $\geq$ 7 days with or without active bleeding, OR <50,000 for $\geq$ 7 days with clinically significant bleeding b  |                     | Decrease 1 dose level |

a Anetumab ravtansine dose reduction by 1 dose level translates to a change from 6.5 mg/kg (BW) Q21D to 5.5 mg/kg Q21D, or from 5.5 mg/kg Q21D to 4.5 mg/kg Q21D.

b Clinically significant bleeding is that which requires platelet transfusion.

c Febrile neutropenia is defined as ANC < 500 with fever of  $>38.3^{\circ}\text{C}$  [ $101^{\circ}\text{F}$ ] or a sustained body temperature of  $\geq 38.0^{\circ}\text{C}$  [ $100.4^{\circ}\text{F}$ ] for more than one hour).

If anetumab ravtansine treatment modification is required due to a nonhematological TEAE, and the continuation of anetumab ravtansine treatment is appropriate at the investigator's discretion, then the anetumab ravtansine dose will be reduced after CTCAE Grade 4 nonhematologic TEAE and Bayer Grade 3 corneal epitheliopathy, or either reduced or maintained at the investigator's discretion after CTCAE Grade 3 non-hematologic TEAE or Bayer Grade 2 corneal epitheliopathy change (attached table).

The anetumab ravtansine dose reduction due to nonhematological TEAEs will be performed by 1 mg/kg Q21D as appropriate, i.e., from 6.5 mg/kg Q21D to 5.5 mg/kg Q21D, or from 5.5 mg/kg Q21D to 4.5 mg/kg Q21D.

If treatment interruption is caused by a CTCAE Grade 2 or 3 anetumab ravtansine infusion related reaction or other CTCAE Grade 2 or 3 hypersensitivity events deemed at least possibly related to anetumab ravtansine, treatment may be restarted at the time determined at the investigator's discretion. Retreatment should be started at the infusion rate reduced by 50%, along with anti-allergic prophylaxis (e.g., antihistamines, acetaminophen, and / or corticosteroids) chosen at the investigator's discretion (but not to exceed 42 days since last dose) or according to institutional guidelines.

Treatment with anetumab ravtansine should be withdrawn if a TEAE resolved to CTCAE Grade  $\leq 1$  (or Bayer severity Grade  $\leq 2$  for corneal epitheliopathy) in  $>42$  days after the last dose of anetumab ravtansine.

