#### 7.6 Definition of DLT

Dose-limiting toxicity (DLT) will be defined as an AE occurring in Cycle 1 of the study, attributed (definitely, probably, or possibly) to treatment and meeting the following criteria:

- Grade 4 ANC  $\geq 7$  days or  $\geq$ Grade 3 ANC of any duration with fever  $> 38.3^{\circ}\text{C}$ .
- Grade 4 platelet count or Grade 3 platelet count associated with bleeding.
- AST/ALT/ alkaline phosphatase  $\geq$  Grade 3 if total bilirubin  $< 1.5 \times \text{UNL}$ .
- AST/ALT/alkaline phosphatase  $\geq 2.5 \times \text{UNL}$  together with  $\geq$  Grade 2 total bilirubin ( $> 1.5 \times \text{UNL}$ ).
- Other  $\geq$  Grade 3 non-hematologic toxicities (except transient asymptomatic electrolyte abnormality and nausea, vomiting or diarrhea untreated with anti-emetic support or anti-diarrheal agents, respectively).

Grade 3 laboratory abnormalities without clinically significant sequel (e.g., amylase elevation, etc) will NOT be considered DLT.

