#### 8.11 Hematological TEAEs requiring treatment modification

- ANC  $<500/\text{mm}^3$  (CTCAE Grade 4) for  $\geq 7$  days
- Febrile neutropenia (ANC  $<1000/\text{mm}^3$  and a single body temperature reading of  $>38.3^\circ\text{C}$  ( $\geq 101^\circ\text{F}$ ) or a sustained body temperature of  $\geq 38.0^\circ\text{C}$  ( $\geq 100.4^\circ\text{F}$ ) for more than 1 hour
- Platelet count  $<25,000/\text{mm}^3$  (CTCAE Grade 4) for  $\geq 7$  days regardless of the presence of active bleeding or platelet count  $> 50,000/\text{mm}^3$  (CTCAE Grade  $\geq 3$ ) with clinically significant bleeding (i.e., bleeding requiring platelet transfusion)

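### The 8.17 restart-dose table requires neutrophil and platelet toxicity together before a reduction, so isolated events that 8.11 treats as separate triggers have no matching row or an ambiguous one

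*Combined protocol and SAP*

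**What the plan says.** Section 8.1 defines the events requiring modification as any one of those listed. Section 8.11 gives three haematological bullets:

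- ANC <500 for ≥7 days;
- febrile neutropenia, with ANC <1000;
- platelets <25,000 for ≥7 days regardless of bleeding, or a Grade ≥3 count "with clinically significant bleeding (i.e., bleeding requiring platelet transfusion"), with no duration attached.

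Section 8.16 says that if treatment continues after a haematological event, the dose is adjusted according to the table that follows. That table, in 8.17, has three rows:

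- **No change** (SOC Investigations, labelled Grade 2): "Neutrophil count decrease >500 or <500 for <7 days AND Platelet count decreased" ≥25,000.
- **Decrease one level** (Investigations, GRADE left without a number): ANC <500 for ≥"7 days AND Platelet count decreased <25,000 for" ≥7 "days with or without active bleeding, OR <50,000 for" ≥7 days with clinically significant bleeding.
- **Decrease one level** (Blood and Lymphatic, Grade 3): "Febrile neutropenia AND Platelet count <25,000 for" ≥7 days, followed by the same bleeding alternative.

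Footnote c adds: "Febrile neutropenia is defined as ANC < 500 with fever of" >38.3°C, or sustained ≥38.0°C. Footnote a defines one level as 6.5 to 5.5, or 5.5 to 4.5 mg/kg.

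**The concern.** The trigger list and the dose table do not fit together. A patient with one haematological toxicity meets a trigger in 8.11 and is sent to 8.17 for the restart dose, but the reduction rows ask for two toxicities at once.

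The table also conflicts with 8.11 in two smaller ways. It lowers the febrile neutropenia threshold from ANC <1000 to <500, and it adds a 7-day duration to the bleeding criterion.

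At stake is the dose given to an individual patient after a serious marrow toxicity. Investigators could handle the same event differently. The section on dose re-escalation makes a haematological reduction irreversible, so both under-reduction and unnecessary reduction have consequences.

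**Working it through.** There is no sample-size or error-rate figure to reproduce. The check is whether each 8.11 trigger reaches exactly one action in 8.17.

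**Rules from 8.17**

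- N (no change) = (ANC >500, or <500 for <7 days) and platelets ≥25,000.
- A = ANC <500 for ≥7 days (second row), or febrile neutropenia with ANC <500 (third row, footnote c).
- B = platelets <25,000 for ≥7 days.
- C = platelets <50,000 for ≥7 days with bleeding that needs platelet transfusion.

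Each decrease row reads A AND B OR C. It can be grouped as A AND (B OR C), or as (A AND B) OR C.

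**Result by event**

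The other cell line is normal in every line except the last. N is applied to its criteria text only.

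| Event | A AND (B OR C) | (A AND B) OR C |
|---|---|---|
| ANC <500 ≥7 d, no fever | no row | no row |
| Febrile neutropenia, ANC <500 ≥7 d | no row | no row |
| Febrile neutropenia, ANC <500 <7 d | N text | N text |
| Febrile neutropenia, ANC 500-1000 | N text | N text |
| Platelets <25,000 ≥7 d, no bleeding | no row | no row |
| Platelets <25,000 ≥7 d, bleeding | no row | decrease |
| Platelets 25,000-50,000 ≥7 d, bleeding | N text | N text and decrease |
| Platelets 25,000-50,000 <7 d, bleeding | N text | N text |
| Platelets <25,000 with bleeding, all <50,000 for <7 d | no row | no row |
| ANC <500 ≥7 d and platelets <25,000 ≥7 d | decrease | decrease |

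The entries marked N text depend on the label columns. If the Grade 2 label controls, a Grade 3 platelet count with bleeding drops out of the no-change row. If the SOC or GRADE column controls, so does febrile neutropenia. Except where the second grouping gives a decrease, the result is then no row. The Grade 2 label is itself unreliable, because that row includes ANC <500, which 8.11 calls Grade 4.

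**Internal logic**

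The no-change row requires both conditions. Its complement is ANC <500 for ≥7 days OR platelets <25,000. The second row uses the same limits joined by AND, which leaves the isolated events between the two rows.

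**Frequency**

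Section 1.22 gives monotherapy data only.

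- At 6.5 mg/kg Q3W expansion, 15 of 32 patients had a reduction, with no haematological cause listed: 0/32, exact 95% upper limit 1 − 0.025^(1/32) = 10.9%.
- Over 45 + 32 + 34 + 36 = 147 patients, one reduction is listed for neutropenia: 1/147 = 0.7% (exact 95% CI 0.02% to 3.7%). Many escalation patients were at low doses.
- Section 15.17 lists platelet count decreased in 21.1%, grade not given.

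No rate is given for the combination.

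**Does the proposed correction close the gaps?**

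- Neutrophil and fever states: ANC ≥1000 (1), plus 500-1000, <500 for <7 d and <500 for ≥7 d, each with or without fever (6), total 7.
- Platelet states: ≥50,000 (1); 25,000-50,000 by duration and bleeding (4); <25,000 for <7 d, by whether <50,000 lasted ≥7 d and by bleeding (4); <25,000 for ≥7 d by bleeding (2); total 11.
- 7 × 11 = 77 states. Non-triggering states number 3 × 5 = 15, so 77 − 15 = 62 meet an 8.11 trigger (bleeding criterion read as <50,000).

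With OR in the decrease rows, febrile neutropenia at ANC <1000, and febrile neutropenia and bleeding excluded from no change:

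- Keeping 7 days on bleeding gives one action in 56 of 62. The other 3 × 2 = 6 are all bleeding for <7 days.
- Removing the 7 days gives one action in 62 of 62.
- Of the 15 others, 9 are no change and 6 (platelets <25,000 for <7 d, no bleeding) have no row. Assigning those 6 closes all 77.

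The grid tests completeness and says nothing about frequency. It does not include current dose: at 4.5 mg/kg footnote a offers no lower step.

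**The case against.** The strongest reply is that 8.0 already covers this. It tells the investigator to dose on the greatest reduction needed for any single adverse event, and it leaves reduction and resumption to judgment. Footnote a fixes the size of a step. Restart requires resolution to Grade 1 (8.16), and resolution later than 42 days means withdrawal. These are real safeguards and make a sensible decision likely. They do not say which isolated haematological events call for a step down. Section 8.0 also tells sites to follow the modification table strictly, and 8.17 writes out the choice to reduce or maintain only for non-haematological events.

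A second reply is that a hold without reduction may be intended, since 8.11 requires a modification and a hold is one. That is possible, but the table would need to say so.

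Third, the DLT definition in 7.6 counts "Grade 4 platelet count or Grade 3 platelet count associated with bleeding" and, separately, at least "Grade 3 ANC of any duration with fever" as single events. This favours a single-event reading, but only weakly. Section 7.6 governs cohort escalation, and it already differs from 8.11 by counting Grade 4 platelets without a duration.

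A reader might infer that the protocol orders an unchanged dose after febrile neutropenia or a platelet bleed. The documents do not support that as settled text, because it requires setting aside the Grade 2 label and, for febrile neutropenia, the SOC column. A reader might also infer that every isolated event lacks a reduction. Bleeding at platelets <50,000 for ≥7 days does reach one if the final OR stands alone, although at 25,000-50,000 it then meets the no-change text as well.

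**Conclusion.** The table fails its own triggers and should be corrected. Two gaps hold under either grouping and do not depend on the label columns: isolated ANC <500 for ≥7 days, and isolated platelets <25,000 for ≥7 days without bleeding. Isolated febrile neutropenia (ANC 500-1000, or <500 for <7 days) and short-duration bleeding at 25,000-50,000 never reach a reduction. Whether they mean no change or no row depends on which columns control. The mismatch in the febrile neutropenia threshold and the added 7-day bleeding duration are plain from the text.

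The reach is small. Few patients are likely to be affected, assuming the monotherapy experience is some guide to the combination. This is a correction to an individual dosing rule. It would be wrong to infer bias in DLT counting, the MTD or the response conclusions, since none of these uses the 8.17 table.

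Section 8.11 also reads '> 50,000' for the Grade ≥3 platelet count. One inequality sign in machine-read text is not enough to call an error, so it needs checking against the source.

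**What to change.** - In the two decrease rows, replace AND with OR, or give each 8.11 criterion its own row and action. Where a hold without reduction is intended, state it. That choice belongs to the investigators, and it matters because a haematological reduction cannot be reversed.
- Exclude febrile neutropenia, and clinically significant bleeding at platelets <50,000, from no change.
- Add platelets <25,000 for <7 days without bleeding to no change, or state another action.
- Use one febrile neutropenia threshold (8.11 uses ANC <1000).
- Remove the 7-day condition from the bleeding criterion to match 8.11.
- Correct the Grade 2 label and the blank GRADE entry.
- State the action for a patient already at 4.5 mg/kg.
- Check '> 50,000' in 8.11 against the source, and correct it to <50,000 if it is printed that way.

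The cost is an amendment to one table, one footnote and possibly one bullet. No extra patients or data are needed.

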### **Dose re-escalation**

Dose re-escalation for anetumab ravtansine after dose reduction is not allowed, except reescalation after dose reduction for corneal epitheliopathy if the first Grade 3 event resolves to Grade  $\leq 2$  within 21 days and does not recur.

## **8.2 Treatment Delay and Dose Reduction of Atezolizumab**

### **8.21 General AE Management and Dose Modification Guidelines**

There will be no dose reduction for atezolizumab in this study. Patients may temporarily suspend study treatment for up to 84 days (12 weeks) beyond the scheduled date of delayed infusion if study drug-related toxicity requiring dose suspension is experienced. If atezolizumab is held because of AEs for  $\geq 84$  days beyond the scheduled date of infusion, the patient will be discontinued from atezolizumab and will be followed for safety and efficacy as specified in this protocol.

If a patient must be tapered off steroids used to treat AEs, atezolizumab may be held for additional time beyond 84 days (12 weeks) from the scheduled dose until steroids are discontinued or reduced to a prednisone dose (or dose equivalent) of 10 mg/day. The acceptable length of interruption will be at the discretion of the investigator.

Dose interruptions for reasons other than toxicity, such as surgical procedures, may be allowed.

Any toxicity associated or possibly associated with atezolizumab treatment should be managed according to standard medical practice. Additional tests, such as autoimmune serology or biopsies, may be used to determine a possible immunogenic etiology. Although most immune-related adverse events (irAEs) observed with immunomodulatory agents have been mild and self-limiting, such events should be recognized early and treated promptly to avoid potential major complications (20) (Appendix C). Discontinuation of atezolizumab may not have an immediate therapeutic effect, and there is no available antidote for atezolizumab. In severe cases, immune-related toxicities may be acutely managed with topical corticosteroids, systemic corticosteroids, or other immunosuppressive agents. The investigator should consider the benefit-risk balance prior to further administration of atezolizumab. In patients who have met

the criteria for permanent discontinuation, resumption of atezolizumab may be considered if the patient is deriving clinical benefit and has fully recovered from the immune-related event.

Patients can be re-challenged with atezolizumab ONLY after careful consideration of benefit- risk balance and medical judgment by the trial Principal Investigator. Atezolizumab may NOT be resumed if the patient experiences any of the following events, regardless of benefit:

- Grade 3 or 4 pneumonitis
- AST or ALT  $>5\times$ ULN or total bilirubin  $>3\times$ ULN
- Grade 4 diarrhea or colitis
- Grade 4 hypophysitis
- Any grade myasthenic syndrome/myasthenia gravis, Guillain-Barré, or meningoencephalitis
- Grade 3 or 4 ocular inflammatory toxicity
- Grade 4 or any grade of recurrent pancreatitis
- Grade 3 or 4 infusion-related reactions
- Grade 4 rash

Treatment may, under limited and compelling circumstances, be resumed in patients who have recovered from the following events after consultation with the trial Principal Investigator:

- Grade 2 pneumonitis
- Grade 2 ocular inflammatory toxicity
- Grade 2 infusion-related reactions

For detailed information regarding management of adverse events associated with atezolizumab, please refer to the most current version of the Atezolizumab Package Insert and the FDA product label.

The primary approach to grade 1 to 2 irAEs is supportive and symptomatic care with continued treatment with atezolizumab; for higher-grade irAEs, atezolizumab should be withheld and oral and/or parenteral steroids administered. Recurrent grade 2 irAEs may also mandate withholding atezolizumab or the use of steroids. Assessment of the benefit-risk balance should be made by the investigator, with consideration of the totality of information as it pertains to the nature of the toxicity and the degree of clinical benefit a given patient may be experiencing prior to further administration of atezolizumab. Atezolizumab should be permanently discontinued in patients with life-threatening irAEs.

Patients should be assessed clinically (including review of laboratory values) for toxicity prior to, during, and after each infusion. If unmanageable toxicity due to atezolizumab occurs at any time during the study, treatment with atezolizumab should be discontinued.

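### Section 8.21 forbids restarting atezolizumab after Grade 3 ocular inflammation or pneumonitis, but the table under 8.226 allows it after PI consultation

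*Combined protocol and SAP*

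**What the plan says.** Section 8.21 first gives a general permission: a patient who met the criteria for permanent discontinuation may be considered for re-treatment if benefiting and fully recovered. It then reserves any re-challenge to the judgment of the trial Principal Investigator, and follows with an absolute list: "Atezolizumab may NOT be resumed if the patient experiences any of the following events, regardless of benefit". Among the entries are "Grade 3 or 4 pneumonitis", "Grade 3 or 4 ocular inflammatory toxicity" and "Grade 4 diarrhea or colitis".

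A second list in 8.21 names the events after which treatment may, in limited circumstances, "be resumed in patients who have recovered from the following events after consultation with the trial Principal Investigator". For the two organ systems at issue it contains only "Grade 2 pneumonitis" and "Grade 2 ocular inflammatory toxicity".

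Section 8.226 repeats the general permission for any event that the table marks for permanent discontinuation, subject to PI consultation. The table then gives rules by event and grade:

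- **Uveitis or retinopathy, Grade 3 or 4:** discontinue permanently. A Grade 3 patient can restart once the trial PI has been consulted; a Grade 4 patient cannot restart whatever the benefit.
- **All pulmonary events, Grade 3 or 4:** the same rule, with the same split between Grades 3 and 4.
- **Diarrhea or enterocolitis, Grade 4:** the cell opens with a bar on restarting whatever the benefit, and closes by saying that resumption can be considered in a recovered patient who is benefiting.

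For further detail on managing atezolizumab events, 8.21 tells the reader: "please refer to the most current version of the Atezolizumab Package Insert and the FDA product label".

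**The concern.** The choice is whether to give a checkpoint inhibitor again to a patient who has had a severe immune-related event. Section 8.21 itself notes that stopping the drug may not work at once and that no antidote exists. After Grade 3 uveitis or Grade 3 pneumonitis, one part of section 8 says never and another says yes with consultation. Whoever restarts treatment breaches 8.21, while whoever refuses withholds an option that the table offers.

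These are foreseeable events. Section 15.27 lists colitis and diarrhea among toxicities above 10%, and pneumonitis and intraocular inflammation among those at 1% to 10%, in each case without a grade. All patients have lung cancer, and the synopsis requires slit-lamp examination every 3 weeks because both drugs have eye adverse events. What is at stake is patient safety and uniform treatment.

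**Working it through.** No arithmetic applies. The check sets the texts side by side, confirms that they concern the same events, and looks for a rule that ranks them.

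**Step 1. Compare the rules.**

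| Event | 8.21 list | Table under 8.226 | Result |
|---|---|---|---|
| Ocular inflammation, Grade 3 | Barred | Allowed after PI consultation (uveitis or retinopathy row) | Contradiction |
| Ocular inflammation, Grade 4 | Barred | Barred | Agree |
| Pneumonitis, Grade 3 | Barred | Allowed after PI consultation (pulmonary row) | Contradiction, if the row covers pneumonitis |
| Pneumonitis, Grade 4 | Barred | Barred | Agree |
| Diarrhea or colitis, Grade 4 | Barred | Barred at the start of the cell, permitted at its end | Cell contradicts itself |

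**Step 2. Are these the same events?** Uveitis is an ocular inflammatory toxicity, so the first row compares like with like. The pulmonary row has a broader label than pneumonitis. However, 8.222 names pneumonitis among pulmonary events and sends the reader to the table for their management. The row's Grade 1 cell also directs recurrent pneumonitis to the Grade 3 or 4 instructions, and that cell does not exclude pneumonitis. The documents therefore place pneumonitis inside the row.

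**Step 3. Does PI consultation reconcile the Grade 3 rules?** No. The PI-consultation list in 8.21 stops at Grade 2 for both organ systems. At Grade 3 the bar applies whatever the benefit, so consultation is the table's condition for doing what 8.21 forbids.

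**Step 4. Do the general permissions matter?** The permissive sentences in 8.21 and 8.226 can be read as a general rule to which the 8.21 list is the exception, so they are not counted as conflicts. That reading does not rescue the two Grade 3 cells, which are specific to an event and a grade. A reader could equally take the table as the more specific text.

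**Step 5. Is there a precedence rule?** Three candidates were examined.

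- Section 8.0 asks for strict adherence to a table that it does not identify.
- Section 8.0 also leaves resumption to investigator judgment, without mention of the 8.21 bar.
- The referral to the package insert and label ("please refer to the most current version of the Atezolizumab Package Insert and the FDA product label") ranks no protocol text against another, and the content of those sources is not in the documents.

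None of the three says whether 8.21 or the table governs.

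**Step 6. The Grade 4 diarrhea cell.** Its closing sentence also stands in the Grade 2 and Grade 3 cells of the same row, where it fits. Two explicit bars, one in 8.21 and one opening the cell, stand against one sentence that was probably carried over.

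**The case against.** The strongest case on the other side is that re-challenge is centrally controlled. Section 8.21 reserves it to the trial PI, both Grade 3 cells require PI consultation, and the study is limited to Mayo Clinic. A reader might infer that sites will re-treat in opposite ways without anyone noticing. The documents do not support that, because each Grade 3 case should reach the trial PI. This part of the objection stands, and it lowers the practical risk. It does not remove the conflict, since the PI is handed opposite rules.

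Second, the pulmonary row also covers events such as dyspnea, cough and hypoxia, so its Grade 3 permission could apply to those while the pneumonitis bar stands. That reading is possible, but nothing in the cell states it and the Grade 1 cell points the other way. Even if it is accepted, the Grade 3 ocular contradiction remains.

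Third, a reader might infer that the table simply permits re-treatment after Grade 4 diarrhea or colitis. It does not: the cell opens with the same bar as 8.21. This is a drafting slip in a safety instruction, and less serious than the two Grade 3 reversals.

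A reader might also see a conflict at Grade 2, where the table allows resumption on recovery within 12 weeks without mentioning the PI. That is silence rather than contradiction, and the PI requirement in 8.21 arguably already covers it.

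**Conclusion.** The concern holds for the atezolizumab text. The table reverses the 8.21 bar for Grade 3 uveitis and Grade 3 pneumonitis, and the Grade 4 diarrhea or enterocolitis cell contradicts itself. If the pulmonary row is read as excluding pneumonitis, one Grade 3 reversal and the one inconsistent cell remain. The conclusion rests on uveitis being an ocular inflammatory toxicity and on pneumonitis falling within the pulmonary row. The ocular finding is the firmer of the two.

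No frequency can be attached, because the documents give no rate by grade for these events with this combination. A proportion of contradicted entries would not be informative either: it would depend on how list entries are split, and the table as available lacks a hepatotoxicity entry to which it refers.

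A reader might extend the point to the anetumab ravtansine count-based table in 8.17, where neutrophil and platelet criteria are joined. The documents do not support a firm finding there. That table has blank cells and unanchored footnotes in the available text, and how the criteria should combine is a clinical choice that the protocol does not settle.

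The sample size and the response decision rule are unaffected. The wording should still be corrected, because following a rule stated in the table would re-expose a patient whom 8.21 absolutely excludes.

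**What to change.** Amend section 8 as follows:

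1. State that the list of events in 8.21 after which atezolizumab is never resumed overrides both the 8.226 table and the general resumption permissions in 8.21 and 8.226, unless the clinical team documents a different intent.
2. Delete the Grade 3 resumption wording from the uveitis or retinopathy row. The row also covers retinopathy, so the team should confirm that the bar is meant to reach it.
3. In the pulmonary row, limit the Grade 3 resumption wording to events other than pneumonitis.
4. Delete the closing resumption sentence from the Grade 4 diarrhea or enterocolitis cell.

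If the clinical team did intend to allow Grade 3 re-treatment, 8.21 should be changed instead and the reason recorded.

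A minor correction can go in the same amendment: 8.11 gives the platelet threshold with clinically significant bleeding as above 50,000, whereas the Grade 3 or higher label beside it and the 8.17 table show that below 50,000 is meant.

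The cost is a wording amendment with no design or analysis consequence. The downside is that slightly fewer patients would be eligible for atezolizumab re-treatment.
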